3 STUDY ENDPOINTS

3.1 Primary Endpoints

The primary endpoint is

ORR using the revised response criteria for malignant lymphoma or modified SWAT criteria

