12.3 Revised response criteria for malignant lymphoma

Complete Remission (CR)

1. Complete disappearance of all detectable clinical evidence of disease and disease-related symptom if present prior to therapy.
2. The spleen and/or liver, if considered enlarged prior to therapy on the basis of a physical examination or CT scan, should not be palpable on physical examination and should be considered normal size by imaging studies, and nodules related to lymphoma should disappear.
3. If the bone marrow was involved by lymphoma prior to treatment, the infiltrate must have been cleared on repeat bone marrow biopsy and EBV should be negative by EBV in situ hybridization (ISH).
4. In patients for whom FDG by PET is avid, incorporation of interim PET imaging results as follows: All CR requirements as described above. However, if a patient's PET scan was positive before therapy, a post-treatment residual mass of any size is permitted as long as it is PET negative

Partial Remission (PR)

1. $\geq 50\%$ decrease in sum of the product of the diameters (SPD) of up to 6 of the largest dominant nodes or nodal masses.
2. No increase in the size of the other nodes, liver, or spleen.
3. Splenic and hepatic nodules must regress by $\geq 50\%$ in their SPD or, for single nodules, in the greatest transverse diameter.
4. With the exception of splenic and hepatic nodules, involvement of other organs is usually assessable and no measurable disease should be present.
5. Bone marrow assessment is irrelevant for determination of a PR if the sample was positive prior to treatment. However, if positive, the EBV-positivity should be specified by EBV ISH. Patients who achieve a CR by the above criteria, but who have persistent morphologic or molecular bone marrow involvement will be considered partial responders.
6. No new sites of disease should be observed (e.g., nodes > 1.5 cm in any axis).
7. For patients with FDG-avidity, an interim assessment should be made. For patients whose PET scan was positive before therapy, the post-treatment PET scan should be positive in at

least one previously involved site.

Stable Disease (SD)

1. Failure to attain the criteria needed for a CR or PR, but not fulfilling those for progressive disease
2. PET imaging should be positive at prior sites of disease with no new areas of involvement on the post-treatment PET scan.

Relapsed Disease (RD; after CR) or Progressive Disease (PD; for Patients with PR or SD)

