1. Appearance of any new lesion more than 1.5 cm in any axis during or at the end of therapy, even if other lesions are decreasing in size.
2. At least a 50% increase from nadir in the SPD of any previously involved nodes, or in a single involved node, or the size of other lesions (e.g., splenic or hepatic nodules). To be considered progressive disease, a lymph node with a diameter of the short axis of less than 1.0 cm must increase by $\geq 50\%$ and to a size of 1.5×1.5 cm or more than 1.5 cm in the long axis.
3. At least a 50% increase in the longest diameter of any single previously identified node more than 1 cm in its short axis.
4. If FDG-PET imaging has been obtained, PD should only be designated if the CT criteria for progression have been met and the lesions are PET positive for patients with PET-positive disease prior to therapy. FDG-PET is not mandatory for surveillance of progression.

Response	Definition	Nodal masses	Spleen, liver	Bone marrow
CR	Disappearance of all evidence of disease	(a) FDG-avid or PET positive prior to therapy; mass of any size permitted if PET negative (b) Variably FDG-avid or PET negative; regression to normal size on CT	Not palpable, nodules disappeared	Infiltrate cleared on repeat biopsy; if indeterminate by morphology, IHC should be negative
PR	Regression of measurable disease and no new sites	≥ 50% decrease in SPD of up to 6 largest dominant masses; no increase in size of other nodes (a) FDG-avid or PET positive prior to therapy; one or more PET positive at previously involved site (b) Variably FDG-avid or PET negative; regression on CT	≥ 50% decrease in SPD of nodules (for single nodule in greatest transverse diameter); no increase in size of liver or spleen	Irrelevant if positive prior to therapy; cell type should be specified
SD	Failure to attain CR/PR or PD	(a) FDG-avid or PET positive prior to therapy; PET positive at prior sites of disease and no new sites on CT or PET (b) Variably FDG-avid or PET negative; no change in size of previous lesions on CT		
RD or PD	Any new lesion or increase by ≥ 50% of previously involved sites from nadir	Appearance of a new lesion(s) > 1.5 cm in any axis, ≥ 50% increase in SPD of more than one node, or ≥ 50% increase in longest diameter of a previously identified node > 1 cm in short axis Lesions PET positive if FDG-avid lymphoma or PET positive prior to therapy	> 50% increase from nadir in the SPD of any previous lesions	New or recurrent involvement

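### Appendix 12.3 denies PR to a patient whose PET has turned negative and whose tumour meets the PR size criteria, if a symptom, an enlarged liver or spleen, or a shrunken nodule there still rules out CR

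*Combined protocol and SAP*

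**What the plan says.** Section 3.1 sets the primary endpoint as "ORR using the revised response criteria for malignant lymphoma or modified SWAT criteria", and Section 7.1.6 points to Appendix 12.3 for the lymphoma criteria.

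For a patient who was PET-positive before therapy, Appendix 12.3 says:

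- **CR item 4** keeps the other CR items in force ("All CR requirements as described above") and relaxes them in one respect: "a post-treatment residual mass of any size is permitted as long as it is PET negative". Item 1 still requires clinical evidence of disease and related symptoms to be gone. Item 2 still requires a previously enlarged liver or spleen to be normal and nodules to have disappeared.
- **PR item 7**: "For patients whose PET scan was positive before therapy, the post-treatment PET scan should be positive in at" least one previously involved site. The PR row of the summary table repeats it: "one or more PET positive at previously involved site".
- **PR item 5** gives one route to PR for a near-CR: "Patients who achieve a CR by the above criteria, but who have persistent morphologic or molecular bone marrow involvement will be considered partial responders".
- **SD item 1** is a catch-all: "Failure to attain the criteria needed for a CR or PR, but not fulfilling those for progressive disease".
- **SD item 2** adds: "PET imaging should be positive at prior sites of disease with no new areas of involvement on the post-treatment PET scan". The SD row of the table carries both the catch-all and the PET requirement.
- **PD item 4** allows PD, where PET has been done in such a patient, only with CT progression and PET-positive lesions.

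**The concern.** A positive PET is written as a condition of PR, although it is a sign of residual disease. Losing that sign should move a patient towards CR. If the patient cannot reach CR for a reason unrelated to PET, the text has no PR to fall back on, except for marrow. The better metabolic result is then scored lower than the worse one.

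At stake is the response count. The design turns on small numbers: at least 3 responders among 10 to open stage 2, and at least 8 among 22 to reject the null hypothesis. Conversion to a negative PET is not a remote event here, since the rate of interim PET-negativity is itself a secondary endpoint (Section 3.2).

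**Working it through.** **Step 1. Classify the patient.** Take a baseline PET-positive patient with a negative post-treatment PET, an SPD decrease of at least 50% and no new sites. Let one CR item fail at a time.

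| What remains | CR? | PR? | PD? | SD? | Result |
|---|---|---|---|---|---|
| PET-negative residual mass only | Yes, item 4 | – | – | – | CR, responder |
| Marrow involvement only | No, item 3 | Yes, item 5 | – | – | PR, responder |
| Symptom, or clinical evidence other than a permitted mass | No, item 1 | No, item 7 | No | Item 1 yes, item 2 no | Non-responder |
| Liver or spleen still enlarged, or nodules reduced by at least 50% but not gone | No, item 2 | No, item 7 | No | Item 1 yes, item 2 no | Non-responder |

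The last row is the clearest. PR item 3 treats hepatic and splenic nodules that regress by at least 50% as compatible with PR, and the table places the allowance for a PET-negative mass under nodal masses only. Item 7 alone blocks PR. With one involved site still PET-positive, the patient would be PR.

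**Step 2. Reproduce the design.** Inputs from Section 7.1.1: p0 = 0.20, p1 = 0.45, alpha = 0.05, beta = 0.20, stage 1 rule 2/10, final rule 7/22. The probability of rejecting at true rate p is

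R(p) = Σ (x = 3 to 10) C(10,x) p^x (1−p)^(10−x) × P[Bin(12,p) ≥ max(0, 8−x)].

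- R(0.20) = 0.0492 and R(0.45) = 0.8065.
- A search up to N = 28 returns 2/10, 7/22 as the optimal design.
- 22/(1 − 0.10) = 24.4, rounded up to 25.

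The plan's figures reproduce.

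**Step 3. Illustrate the effect.** Let f be the share of true responders lost through the gap. The documents give no value for f, so the range is assumed. The observed rate becomes 0.45 × (1 − f). The average number lost among 22 patients is 22 × 0.45 × f = 9.9f.

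| f | Rate | Average lost among 22 | Power |
|---|---|---|---|
| 0 | 0.450 | 0 | 0.8065 |
| 2% | 0.441 | 0.2 | 0.7841 |
| 5% | 0.4275 | 0.5 | 0.7476 |
| 10% | 0.405 | 1.0 | 0.6793 |

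The losses are 0.8065 − 0.7841 = 0.022, 0.8065 − 0.7476 = 0.059 and 0.8065 − 0.6793 = 0.127.

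**The case against.** The strongest reply is that the group is small and that the appendix closes most of the apparent gap itself. Several stronger readings are tempting, and the documents do not support them.

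- A reader might infer that missing any CR item opens the gap. It does not. Marrow-only failures go to PR by item 5, and a PET-negative residual mass does not prevent CR.
- A reader might infer that PR items 5 and 7 flatly contradict each other. Item 5 can be read as a specific exception to item 7. It shows that the appendix accepts a near-CR as PR, but writes this down only for marrow.
- A reader might infer that the patient fits no category. SD item 1 is a catch-all. The defect is that SD item 2 contradicts it; a category does exist.
- A reader might infer that the patient is certainly lost from the ORR. That depends on things the plan leaves open. PET is mandatory only at sites with a scanner (Schedule of Events, footnote i). CT continues every 6 weeks after cycle 2 (footnote g). No best-overall-response rule is given, so a PR at an assessment without PET might still count. The verb is also only should.

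Two further points stand. The endpoint rests on a cited published standard that cannot be examined from these documents, so whether the wording is inherited or local is unknown. And the power figures rest on an assumed f; they are not evidence that the ORR is biased.

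None of this helps the patient in the last two rows of the first table: whether called SD or left unclassified, that patient is not a responder at that assessment on the text as written. Leaving the meaning of should to judgement in an open-label, single-arm trial is no remedy.

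**Conclusion.** The point holds in a narrow form. For a baseline PET-positive, now PET-negative patient who meets the PR size criteria but fails CR item 1 or 2, PR item 7 and the table deny PR, and SD items 1 and 2 disagree on what the patient is instead. The patient is a non-responder at that assessment despite a better PET result than an ordinary PR.

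Patients PET-negative at baseline, assessments without PET, and skin disease assessed by mSWAT are unaffected. The direction is conservative: the rule can only withhold responses, so it cannot produce a false claim of activity.

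The size is unknown. Over the assumed 2% to 10%, power falls by about 2 to 13 percentage points. The upper end corresponds to roughly one responder lost per 22 patients on average, and assumes that each affected patient is lost at every assessment. If nobody falls in the gap, the effect is nil. It is still worth correcting, because the fault lies in a stated rule for the primary endpoint and is cheap to repair.

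**What to change.** In Appendix 12.3, amend PR item 7 and the PR cell of the table so that a baseline PET-positive patient who meets the PR size criteria, has a negative post-treatment PET and does not meet every CR item is classed as PR. Reconcile SD item 2 and its table cell with SD item 1, so that the catch-all and the PET condition no longer disagree.

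The cost is a sentence or two and the matching table cells. No new data, visits or scans are needed, and the design figures stay as they are. The one drawback is a local clarification of published criteria. It should therefore be documented as such, checked against the cited source, and fixed before responses are read.

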12.4 Modified SWAT criteria for skin lesions

Definitions of skin lesions

1. Patch: any size lesion without induration or significant elevation above the surrounding uninvolved skin: poikiloderma may be present.
2. Plaque: any size lesion that is elevated or indurated: crusting or poikiloderma may be present.
3. Tumor: any solid or nodular lesion ≥ 1 cm in diameter with evidence of deep infiltration in the skin and/or vertical growth.

Modified SWAT tool

Body Region	% BSA in Body Region	Assessment of Involvement in Patient's Skin		
		Patch*	Plaque†	Tumor‡
Head	7			
Neck	2			
Anterior trunk	13			
Arms	8			
Forearms	6			
Hands	5			
Posterior trunk	13			
Buttocks	5			
Thighs	19			
Legs	14			
Feet	7			
Groin	1			
Subtotal of lesion BSA				
Weighting factor		$\times 1$	$\times 2$	$\times 4$
Subtotal lesion BSA \times weighting factor				

NOTE. mSWAT score equals summation of each column line.

Abbreviations: BSA, body surface area; mSWAT, modified Severity Weighted Assessment Tool.

*Any size lesion without induration or significant elevation above the surrounding uninvolved skin; poikiloderma may be present.

†Any size lesion that is elevated or indurated; crusting, ulceration, or poikiloderma may be present.

‡Any solid or nodular lesion ≥ 1 cm in diameter with evidence of deep infiltration in the skin and/or vertical growth.

Response in skin

T1 Limited patches, papules, and/or plaques covering < 10% of the skin surface; may further stratify into T1a (patch only) v T1b (plaque ± patch)

T2 Patches, papules, or plaques covering ≥ 10% of the skin surface; may further stratify into T2a (patch only) v T2b (plaque ± patch)

T3 One or more tumors (≥ 1 cm diameter)

T4 Confluence of erythema covering ≥ 80% body surface area

Response	Definition
Complete response	100% clearance of skin lesions*
Partial response	50%-99% clearance of skin disease from baseline without new tumors (T ₃) in patients with T ₁ , T ₂ or T ₄ only skin disease
Stable disease	< 25% increase to < 50% clearance in skin disease from baseline without new tumors (T ₃) in patients with T ₁ , T ₂ , or T ₄ only skin disease
Progressive disease ^t	≥ 25% increase in skin disease from baseline or New tumors (T ₃) in patients with T ₁ , T ₂ or T ₄ only skin disease or Loss of response: in those with complete or partial response, increase of skin score of greater than the sum of nadir plus 50% baseline score
Relapse	Any disease recurrence in those with complete response

NOTE. Based on modified Severity Weighted Assessment Tool score.

*A biopsy of normal appearing skin is unnecessary to assign a complete response. However, a skin biopsy should be performed of a representative area of the skin if there is any question of residual disease (persistent erythema or pigmentary change) where otherwise a complete response would exist. If histologic features are suspicious or suggestive of mycosis fungoides/Sézary syndrome (see histologic criteria for early mycosis fungoides⁷), the response should be considered a partial response only.

^tWhichever criterion occurs first.
